2.1.4 Safety endpoints

The safety analysis will be based on the reported adverse events and other safety information, such as clinical laboratory data, vital signs, ECG and physical examination.

Observation period

The observation period will be divided into 4 epochs:

- The **screening** epoch is defined as the time from the signed informed consent date up to the time prior to first administration of the IMP.

- The **treatment** epoch is defined as the time from the first administration of the IMP to the last administration of the IMP + 14 days.
- The **residual treatment** epoch is defined as the time from the last administration of the IMP +15 days to the last administration of the IMP + 98 days.

The treatment-emergent adverse event period will include both **treatment** and **residual treatment** epochs.

- The **posttreatment** epoch is defined as the period of time starting the day after the end of the treatment-emergent adverse event period up to the end of the study (defined as last protocol planned visit or the resolution/stabilization of all serious adverse events and adverse events with pre-specified monitoring).
- The on-study observation period is defined as the time from start of treatment until the end of the study (defined as last protocol planned visit or lost to follow-up or the resolution/stabilization of all serious adverse events and adverse events with pre-specified monitoring).

2.1.4.1 Adverse events variables

Adverse event observation period

- Pretreatment adverse events are adverse events that developed or worsened or became serious during the screening epoch
- Treatment-emergent adverse events are adverse events that developed or worsened or became serious during the treatment-emergent adverse event period
- Posttreatment adverse events are adverse events that developed or worsened or became serious during the posttreatment epoch

All adverse events (including serious adverse events and adverse events with pre-specified monitoring/of special interests) will be coded to a lower-level term (LLT), preferred term (PT), high-level term (HLT), high-level group term (HLGT), and associated primary system organ class (SOC) using the version of Medical Dictionary for Regulatory Activities (MedDRA) currently in effect at Sanofi at the time of database lock.

The occurrence of adverse events (including serious adverse events and adverse events with prespecified monitoring) will be recorded from the time of signed informed consent until the end of the study. **Adverse events of special interest (AESI) and other selected AE groupings** will be searched based on the criteria in [Table 1](#).

Table 1 Criteria for adverse events of special interest and other selected AE groupings

AE Grouping	Criteria
AESI	
Anaphylactic reaction	Anaphylactic reaction algorithmic approach (Introductory Guide for Standardised MedDRA Queries (SMQs) Version 18.1): includes anaphylactic reaction narrow SMQ (20000021) terms; for selection based on occurrence of multiple symptoms, the symptoms must have occurred within 24 hours of each other
Hypersensitivity (medically reviewed)	SMQ hypersensitivity (20000214) narrow search and [AE corrective treatment/therapy='Y' or Action taken with IMP='Drug withdrawn' or Action taken with IMP='Drug interrupted'] followed by blinded medical review (documented process) for selection of relevant systemic hypersensitivity events
Serious injection site reactions or severe injection site reactions that last longer than 24 hours	HLT = 'Injection site reaction' and either with serious status, or with severe status and (AE end date/time - AE start date/time) ≥ 24 hours or ongoing
Severe or serious infection	Primary SOC = 'Infections and infestations' and with severe or serious status
Parasitic infection	The Infection Type 'Parasitic' was checked on eCRF page "Infection Defined as AESI Complementary Form"
Opportunistic infection	The Infection Type 'Opportunistic' was checked on eCRF page "Infection Defined as AESI Complementary Form"
Drug-related hepatic disorder	Drug-related hepatic disorders-Comprehensive search narrow SMQ (20000006)
Pregnancy	Primary SOC = 'Pregnancy, puerperium and perinatal conditions' or PT in (Aborted pregnancy, False negative pregnancy test, Pregnancy test positive, Pregnancy test urine positive, Ectopic pregnancy termination)
Symptomatic overdose with IMP	The question "Is the event a Symptomatic Overdose with IMP?" is answered "Yes" on the eCRF page "Adverse Event"
Symptomatic overdose with NIMP	The question "Is the event a Symptomatic Overdose with NIMP?" is answered "Yes" on the eCRF page "Adverse Event"
Other selected AE grouping	
Injection site reaction	HLT = 'Injection site reaction'
Malignancy	Sub-SMQ (20000091)- Malignant or unspecified tumors
Suicidal behavior	PT in (Completed suicide, Suicidal ideation, Depression suicidal, Suicidal behavior, Suicide attempt)
Partner pregnancy	PT in (Pregnancy of partner, Miscarriage of partner)
Epistaxis/nose bleeding	PT in (Epistaxis, Nasal septum haematoma)
Conjunctivitis (narrow)	PT in (Conjunctivitis, Conjunctivitis allergic, Conjunctivitis bacterial, Conjunctivitis viral, Atopic keratoconjunctivitis)

AE Grouping	Criteria
Conjunctivitis (broad)	PT in (Conjunctivitis, Conjunctivitis allergic, Conjunctivitis bacterial, Conjunctivitis viral, Atopic keratoconjunctivitis, Blepharitis, Dry eye, Eye irritation, Eye pruritus, Lacrimation increased, Eye discharge, Foreign body sensation in eyes, Photophobia, Xerophthalmia, Ocular hyperaemia, Conjunctival hyperaemia)
Hypereosinophilia	HLT = 'Eosinophilic disorders' or PT = 'Eosinophil count increased'

2.1.4.2 Deaths

The deaths observation period are per the observation periods defined above.

- Death on-study: deaths occurring during the on-study observation period
- Death on-treatment: deaths occurring during the treatment-emergent adverse event period
- Death poststudy: deaths occurring after the end of the study

2.1.4.3 Laboratory safety variables

Clinical laboratory data consists of blood analysis, including hematology, clinical chemistry, and urinalysis. Clinical laboratory values after conversion will be analyzed into standard international units and international units will be used in all listings and tables.

Blood samples for clinical laboratories will be taken at Visit 1(Week -4±1), Visit 2 (Week 0), Visit 7 (Week 16), Visit 8 (Week 24), Visit 9 (Week 40), Visit 10(Week 52), Visit 11(Week 64) and early termination unless otherwise specified. The laboratory parameters will be classified as follows:

- Hematology
 - **Red blood cells and platelets and coagulation:** hemoglobin, hematocrit, red blood cell count, platelet count
 - **White blood cells:** white blood cell count, neutrophils, lymphocytes, monocytes, basophils, eosinophils
- Clinical chemistry
 - **Metabolism:** glucose, total cholesterol, total protein, creatine phosphokinase
 - **Electrolytes:** sodium, potassium, chloride, bicarbonate
 - **Renal function:** creatinine, blood urea nitrogen, uric acid
 - **Liver function:** alanine aminotransferase, aspartate aminotransferase, alkaline phosphatase, lactate dehydrogenase, total bilirubin (in case of values above the normal range, differentiation in conjugated and non-conjugated bilirubin), albumin
 - **Pregnancy test:** Serum β -human chorionic gonadotropin (all female patients) will be performed at screening (V1) in women of childbearing potential, and a urine dipstick pregnancy test will be performed at V2 prior to randomization and every 4 weeks

thereafter. A negative result must be obtained at V1 and V2 prior to randomization. In case of positive urinary test the study treatment will be withheld and a serum pregnancy test to confirm the pregnancy should be performed as soon as possible. Pregnancy will lead to definitive treatment discontinuation in all cases.

- **Hepatitis screen:** hepatitis B surface antigen (HBs Ag), hepatitis B Surface antibody (HBs Ab), hepatitis B core antibody (HBc Ab), hepatitis C virus antibodies (HCV Ab), In case of results showing HBs Ag (negative), HBs Ab (negative) and HBc Ab (positive), an HBV DNA testing may be performed prior to randomization to rule out a false positivity if the investigator believes the patient is a false positive, or to clarify the serological status if the investigator finds it unclear to interpret in absence of known HBV infection. In case of results showing HCV Ab (positive), an HCV RNA testing may be performed to rule out a false positivity, if the investigator believes the patient is a false positive.
- **Hepatitis B viral load** will be tested at V2, V7, V8 and V10 for patients in Japan or other countries/regions if there is local regulatory requirement who are HBs Ag negative and HBs Ab positive at screening.
- **HIV screen:** Anti-HIV-1 and HIV-2 antibodies will be tested at Visit 1
- **Anti-nuclear antibody (ANA)** will be tested at Visit 1

Note: Anti-ds DNA antibody will be tested if ANA is positive ($\geq 1:160$ titer).

Technical formulas are described in [Section 2.5.1](#).

2.1.4.4 Vital signs variables

Vital signs, including blood pressure (mmHg), heart rate (beats per minute), respiratory rate (breaths per minute), body temperature (degrees Celsius) and body weight (kg) will be measured at the screening and randomization visits (Visits 1 and 2) and subsequent visits pre-specified in the flowchart. Height (cm) will be measured at screening (Visit 1) only. Vital signs will be measured in the sitting position using the same arm (preferably) at each visit, and will be measured prior to receiving IMP at the clinic visits.

2.1.4.5 Electrocardiogram variables

A standard 12-lead electrocardiogram (ECG) will be performed at the sites at the time points noted in the Study Flowchart ([Section 1.4.1](#)) to monitor any potential abnormality. In case of an abnormal ECG finding, the Investigator should enter details into the e-CRF. At V2, the investigator should use their medical judgment to consider whether the patient is eligible for the study.

2.1.4.6 Physical Examination

Physical examinations will be performed at Visit 1(Week -4±1), Visit 8 (Week 24), Visit 10 (Week 52), and Visit 11 (Week 64) including an assessment of general appearance, skin, eyes,

ear/nose/throat, heart, chest, abdomen, reflexes, lymph nodes, spine, and extremities. All deviations from normal will be recorded, including those attributable to the patient's disease.

2.1.5 Pharmacokinetic variables

Predose serum dupilumab concentrations at Visit 2 (Day 1), dupilumab trough levels at Week 2, Week 4, Week 16, Week 24, Week 40, Week 52/EOT Visit and posttreatment serum dupilumab at Week 64/EOS Visit will be provided.

Anti-dupilumab antibody (ADA) status (negative or titer value, if positive in the ADA assay) at Visit 2 (Day 1), Week 8, Week 16, Week 24, Week 52 and follow up at Week 64 will be provided. Patients who discontinue early from treatment may be asked to return to the clinic to have additional ADA samples collected for analysis based on the overall clinical presentation at that time.

ADA incidence will be classified as the following:

Pre-existing immunoreactivity are defined as:

An ADA positive response in the assay at baseline with all post treatment ADA results negative, OR an ADA positive response at baseline with all post treatment ADA responses less than 4-fold over baseline titer levels.

Treatment-emergent anti-drug antibodies are defined as:

A positive response in the ADA assay post first dose, when baseline results are negative or missing.

Treatment-emergent ADA responses are further classified as Persistent, Indeterminate or Transient

- a) Persistent Response- defined as a treatment-emergent ADA response with two or more consecutive ADA positive sampling time points, separated by greater than (>) 12-week period (84 days) ,with no ADA negative samples in between.
- b) Indeterminate Response- defined as a treatment-emergent response with only the last collected sample positive in the ADA assay
- c) Transient Response - defined as a treatment-emergent response that is not considered persistent OR indeterminate

Treatment-boosted response is defined as:

An ADA positive response in the assay post first dose that is greater-than or equal to 4-fold over baseline titer levels, when baseline results are positive.

Titer values (Titer value category)

- Low (Titer <1000)
- Moderate ($1,000 \leq \text{Titer} \leq 10,000$)
- High (Titer >10,000)

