Blood biomarkers (TARC, eotaxin-3, periostin, serum total IgE)		X							X				X	
Spot urine for biomarker sampling (LTE4 and PGDM and creatinine)	X	X						X	X				X	
██████████ ██████████		X						X	X					
████████████████████████████████████████		X							X					
██████████ ██████████		X												
██████ ████████		X							X				X	
████████████████████████████████████████		X												

- a The run-in period is 28 days in duration to run in any patient on MFNS, and to collect baseline data. Patients receiving rescue medication with SCS or and surgery during this period will not be randomized. V2 will take place 28 days+/-3 days window after V1. Window for subsequent visits is also +/-3 days. Assessments/procedures at a site visit are performed in the following order if applicable: Patient-reported outcomes and other questionnaires; Procedures; Safety and laboratory assessments; IMP administration.
- b Optional interim visits may be scheduled at site for IMP/NIMP supply or IMP administration.
- c Patients who discontinue treatment early will be assessed as soon as possible using the procedures normally planned for the EOT Visit and will be instructed to return to the study site as described in [Section 10.3.1](#).
- d Past medical history including allergic comorbidities (asthma, aspirin sensitivity, allergic rhinitis etc.). Surgeries for NP will be assessed including number, type and dates of sino-nasal surgeries, polypectomies in the past. Systemic corticosteroids (SCS) use (number of courses, doses, way of administration and duration) in the past 2 years before V1 and/or contraindication/intolerance to SCS, as well as long term antibiotics use (>2weeks) in the previous year will be entered in the e-CRF. NERD: NSAID (non-steroid anti-inflammatory drug) Exacerbated Respiratory Disease will be assessed through a specific questionnaire [Appendix F](#).

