### 10.1 VISIT SCHEDULE

This section describes how the visits are carried out, in chronological order (according to the flow chart [Section 1.2](#) and identical to the order shown in the e-CRF):

The clinical trial consists of three periods, using an add-on therapy approach to INCS:

- Run-in Period (28 days+/- 3 days; V1).
- Randomized treatment period (up to 52 weeks +/- 3 days; Visits 2-10).
- Post-treatment Period (12 weeks; +/- 3 days V11).

The study visits occur on the planned dates (relative to the first injection), as scheduled. The visit schedule should be adhered to within the  $\pm 3$  day visit window.

If a patient is prematurely discontinued from treatment, every attempt should be made for the patient to return to the study site as soon as possible after last IMP administration to perform all assessments planned at the EOT visit and patients will be asked and encouraged to return to the study site for the visit scheduled as described in [Section 10.3.1](#) (early discontinuation) for a 12-week follow up.

Prior to all screening assessments, after discussion of participation in the study, the written consent form [REDACTED] must be signed and dated (see [Section 12.2](#)). At selected sites, requirements for collection of samples for a nasal biomarkers substudy will be included in a separate written informed consent.

Although the screening assessments for this study are grouped under the heading of a single visit in this protocol, it is possible for them to be performed over more than 1 site visit if necessary, as long as the run-in period window prior to Day 1 (V2) is respected. These patients do not need to sign a new consent form and be allocated a new patient number within this same window.

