##### **11.4.4.2 Anti-drug antibodies analysis**

Incidence of positivity in the ADA assay will be assessed on samples collected, as absolute occurrence (n) and percent of patients (%), presented by treatment groups. Listing of all ADA titer levels will be provided for patients positive in the ADA assay. Samples positive in the ADA assay will be further characterized for the presence of anti-dupilumab neutralizing antibodies.

Plots of concentrations of functional dupilumab will be examined and the potential influence of ADA on individual concentration-time profiles will be evaluated. Assessment of the potential impact of ADA on safety and efficacy may be provided.

ADA at baseline will be summarized by:

- Number (%) of patients with a baseline sample negative in the ADA assay.
- Number (%) of patients with a baseline sample positive in the ADA assay (Pre-existing immunoreactivity).

Total subject number (%) will be provided for the following:

- Number (%) of patients with treatment-emergent positive response in the ADA assay. (ADA incidence).
- Number (%) of transient treatment-emergent positive patients.
- Number (%) of persistent treatment-emergent positive patients.

- Number (%) of treatment-boosted positive patients.
- Number (%) of undetermined treatment-emergent positive patients.

Titer values (Titer value category).

The minimum titer for samples positive in the ADA assay is based on the minimum required dilution of the assay.

- Low (Titer <1000).
- Moderate ( $1\ 000 \leq \text{Titer} \leq 10\ 000$ ).
- High (Titer >10 000).

Definitions of pre-existing immunoreactivity, treatment emergent, persistent response, transient response, treatment boosted, and undetermined response will be specified in the statistical analysis plan (SAP).

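### The strict more-than-84-days rule for persistent ADA labels patients negative at Week 24 and positive at both Weeks 52 and 64 as transient on the planned schedule

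*SAP*

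**What the plan says.** SAP section 2.1.5 splits treatment-emergent ADA into three classes.

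- Persistent needs "two or more consecutive ADA positive sampling time points", which must be "separated by greater than (>) 12-week period (84 days", with no negative sample between them.
- Indeterminate is "defined as a treatment-emergent response with only the last collected sample positive in the ADA assay".
- Transient is the residual class: "defined as a treatment-emergent response that is not considered persistent OR indeterminate".

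The same section gives the sampling plan: ADA status at Day 1 and at "Week 8, Week 16, Week 24, Week 52 and follow up at Week 64 will be provided". The flow chart in Protocol section 1.2 places Week 52 on Day 365 and Week 64 on Day 449, and its footnote adds "Window for subsequent visits is also +/-3 days". Protocol section 10.1 anchors every visit to the start of dosing: "The study visits occur on the planned dates (relative to the first injection), as scheduled".

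The protocol has no competing definition. Its section 11.4.4.2 lists the classes and says the terms up to and including "undetermined response will be specified in the statistical analysis plan (SAP"). The SAP does not say whether separation is measured on nominal visits or actual sample dates.

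**The concern.** The threshold coincides with the spacing of the last two planned samples. Exactly 12 weeks fails a strict more-than-12-weeks rule, so two positives at Weeks 52 and 64 cannot by themselves make a response persistent. They also rule out indeterminate, because more than the last sample is positive. Only transient is left, a label that suggests the antibodies went away, for a patient whose last two samples were both positive.

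The rule also behaves oddly as data accumulate. A patient whose only positive is at Week 52, with no Week 64 sample yet, is indeterminate. A second positive 84 days later turns that patient transient.

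No ADA sample is planned between Weeks 24 and 52. ADA arising in those 28 weeks is first seen at Week 52, which is the onset the rule mishandles. SAP section 2.4.6.1.2 commits to counts for each class, peak-titer summaries by class and plots of drug concentration by ADA classification, so the label reaches planned outputs.

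**Working it through.** **Inputs.** Threshold and class definitions: SAP 2.1.5. Sampling days 57, 113, 169, 365 and 449 (Weeks 8, 16, 24, 52 and 64) and the ±3-day window: Protocol 1.2.

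**The plan's own figure.** 12 weeks × 7 = 84 days, as stated.

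**Nominal gaps between neighbouring samples.**

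- Weeks 8 to 16: 113 − 57 = 56 days
- Weeks 16 to 24: 169 − 113 = 56 days
- Weeks 24 to 52: 365 − 169 = 196 days
- Weeks 52 to 64: 449 − 365 = 84 days

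Only the last gap sits on the boundary.

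**All result patterns.** Five samples, each positive or negative, give 32 patterns. Assume baseline negative or missing, no missing samples and nominal days. Measure separation from the first to the last positive of an uninterrupted run, the reading most favourable to persistent. The SAP rule gives 10 persistent, 20 transient, 1 indeterminate and 1 never positive.

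Eight patterns have both Weeks 52 and 64 positive:

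- Week 24 also positive (4 patterns): the run spans at least 449 − 169 = 280 days, so all are persistent.
- Week 24 negative (4 patterns, any result at Weeks 8 and 16): the final run spans 84 days. Since 84 is not greater than 84, the response is not persistent. It is not indeterminate, so it is transient.

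Replacing > with ≥ moves exactly these 4 patterns to persistent, and the totals become 14 persistent, 16 transient and 1 indeterminate.

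**Actual dates.** With offsets *a* at Week 52 and *b* at Week 64, each from −3 to +3 days, the gap is 84 + *b* − *a*. The minimum is 84 − 6 = 78 and the maximum 84 + 6 = 90. Of 7 × 7 = 49 offset pairs, 21 give less than 84, 7 give exactly 84 and 21 give more. If all pairs are equally likely (an assumption), 28/49 = 57% are transient and 21/49 = 43% persistent, for the same assay results.

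**Early loss of follow-up.** A patient negative at Week 8, positive at Weeks 16 and 24 and then lost has positives 56 days apart. That patient is also transient, with no later negative. This is the same gap in the definitions, without the 84-day tie.

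**The case against.** The strongest reply is that this is a boundary clarification in a descriptive sub-classification, and several parts of that reply stand.

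- **Scope.** A reader might infer that anyone positive at the last two samples is mislabelled. With complete sampling that is not so: the tie affects only final runs that start at Week 52.
- **Safety.** A reader might infer that the safety analyses are distorted. The ADA variables that SAP 2.4.6.1.2 names for safety are peak titer, neutralizing status, treatment-emergent and treatment-boosted ADA. That list is given as examples, but no safety analysis by persistent or transient class is specified.
- **PK and efficacy associations.** The SAP says only that these may be explored. The efficacy association concerns the co-primary endpoints, which are Week 24 changes, while the positive run at issue begins after Week 24. Relabelling these patients says little about any ADA effect on those endpoints.
- **Extra sampling.** Patients ADA-positive at their last visit may be asked back for further samples (Protocol 1.2 footnote and 9.5.1.1). A later positive would extend the run past 84 days. This is discretionary, so it reduces the problem without closing it.
- **Database lock.** Under SAP section 4 the main analysis locks when all patients have completed Week 52 or discontinued, and later data go to a CSR addendum. The mislabelling reaches the main report only through Week 64 samples collected before that lock.
- **The 57%.** This is not a figure from the documents. It needs actual dates and a uniform visit distribution, and the SAP specifies neither.

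None of this makes transient a correct label for a response still positive at the last planned sample.

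**Conclusion.** The point holds within these limits. On nominal days, every patient negative at Week 24 and positive at both Weeks 52 and 64 is classed as transient, in 4 of the 8 patterns with both last samples positive. On actual dates, a shift of a few days decides between transient and persistent. Nothing else in the protocol or SAP repairs the definition.

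The consequences are confined to the persistent, transient and indeterminate counts, the titer summaries and concentration plots by class, and the exploratory PK and efficacy associations. Where Week 64 samples fall after the lock, they appear in the CSR addendum. The documents do not support a stronger claim: overall treatment-emergent ADA incidence, the efficacy tests, alpha and sample size are unchanged. The documents also give no expected number of affected patients, so 57% must not be read as a share of ADA-positive patients in the trial. The pattern counts describe possible result sequences, not how often they occur.

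**What to change.** Change the definitions in SAP 2.1.5 in two places.

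1. Persistent: consecutive positives, with no negative between, at least 12 weeks apart by scheduled visit. Use ≥ instead of >, and state nominal visits as the single basis. On actual dates, ≥ 84 alone would still miss in-window gaps of 78 to 83 days. The other nominal spans (56, 112 for Weeks 8 to 24, and 196 days) lie well away from 84, so among scheduled samples only the Week 52 to 64 pair moves.
2. Indeterminate: any treatment-emergent response whose final uninterrupted run of positives includes the last collected sample but is too short to be persistent. This covers early withdrawals such as the Weeks 16 and 24 case.

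The second change also moves responses with an earlier short positive spell, a negative at Week 52 and a positive at Week 64. There are 8 patterns with Week 52 negative and Week 64 positive. One is already indeterminate (all earlier samples negative) and one is persistent (Weeks 8, 16 and 24 all positive, 169 − 57 = 112 days), so 8 − 2 = 6 move from transient to indeterminate. With both changes the totals are 14 persistent, 16 − 6 = 10 transient and 1 + 6 = 7 indeterminate.

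The text should also say how early-termination and extra follow-up samples are counted. The cost is one SAP definition and its programming, with no new data and no change to any test.
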